# 3.0 STUDY INVESTIGATIONAL PLAN

The details of the study design, AIRWISE: Assessment In a Real World setting of the effect of Inhaled Steroid-based triple therapy versus the combination of tiotropium and olodaterol on reducing chronic obstructive pulmonary disease (COPD) Exacerbations, are fully described in the study protocol (Section 4, Study Design).

# 3.1 Patient Randomization

Enrolled study patients will be randomized to either Stiolto Respimat or triple therapy in a 1:1 ratio. Development and validation of the randomization process is described in Appendix A.

# 3.2 Evaluation Schedule and Definitions

Consistent with the naturistic design, this study does not have a rigid visit schedule. It is anticipated that participating patients will undergo medical evaluation at regular intervals as part of standard clinical practice. However, the only required study visits are a baseline visit and a final end of study (EOS) visit at 12 months post enrollment.

# 3.2.1 Baseline

Baseline is defined as the first study visit date. After eligible patients interested in participating provide written informed consent, they will be randomized to either Stiolto Respimat or triple therapy. A blood sample will be drawn at the baseline visit for a complete blood count (CBC) including differential white cell count or historical CBC can be used if available. Additionally, participating patients will complete the COPD Assessment TestTM (CAT). The following data will be collected at baseline and recorded in the electronic Case Report Form (eCRF): eligibility criteria, demographics, selected pre-specified comorbid conditions, COPD history (diagnosis date, number of moderate and severe COPD exacerbations in the 12 months prior to study enrollment, pre-study COPD therapy, selected pre-specified COPD concomitant medications and reason for therapy escalation), blood eosinophil count, smoking status, CAT responses and study treatment.

# 3.2.2 On Study Visits

While there are no required on study visits, it is anticipated that patients who are being treated for COPD will undergo medical evaluation at regular intervals. On study data collection will occur as patients are followed according to their treating physician's routine clinical practice and judgment for the 12 month study period, including routine clinical visits, other patient contact (e.g., phone or e-mail), contact with another treating physician, or receipt of records. Data collected will include COPD exacerbations, selected pre-specified COPD concomitant medications, changes to study treatment, adverse events (AEs) leading to study treatment discontinuation, dose modification or trial withdrawal, and any serious adverse events (SAEs). Patients will be followed and data will be collected at each contact for the full 12 month study period.

# 3.2.3 EOS

The planned EOS visit will be 12 months after baseline. Data collection at EOS will include COPD exacerbations, selected pre-specified COPD concomitant medications, changes to study treatment, AEs leading to study treatment discontinuation, dose modification or trial withdrawal, and any SAEs. For the purposes of analysis, EOS visits up to 12 months (+30 days) post-Baseline will be included. EOS visits that occur after this window will be considered for inclusion in analysis on a case by case basis. However, only COPD exacerbations with an onset date up to and including 12 months post-Baseline will be included in analysis.

# 4.0 STATISTICAL METHODOLOGY

# 4.1 General Considerations

Statistical programming and analyses will be performed using SAS® version 9.4 or higher. Some analyses will utilize prospectively collected data from study sites. Other analyses will use administrative claims data from patients on the set health plans (i.e., ) and targeted non-plans.

Patient characteristics, treatments and outcomes will be tabulated and summarized with descriptive statistics. The descriptive statistics will include means, medians, standard deviation (SD), minimum, maximum and interquartile range (IQR) (difference between the 25th and 75th percentiles) for continuous variables and counts and relative frequencies for categorical data. The descriptive statistics will be presented for the study population overall and by treatment arm.

Raw data (i.e., minimum and maximum values presented for range in continuous variables) will be reported out to the precision with which it was collected. Means will be reported to 1 decimal place more than the raw data. The standard deviation will be reported to 1 decimal place more than the mean. Percentages will be reported to 1 decimal place. Trailing zeros will be presented to maintain a consistent level of precision, e.g. 2.0 rather than 2.

# 4.2 Sample Size Determination

The sample size calculated for this study is 3200 patients with approximately 1600 patients in each treatment group. Sample size calculations are summarized in the study protocol (Section 6.3, Sample Size Determination). Due to early study termination, the actual sample size will be approximately 703 patients.

# 4.3 Missing Data

Except where otherwise noted, missing data will not be imputed and will be excluded from calculations.

# 4.4 Data Definitions and Calculations

# 4.4.1 Demographics

Age will be presented in years based on the patient's birth date and Baseline visit date. The age (years) will be categorized as follows:

- $\leq 55$  years
- >55 to  $\leq 65$  years
- >65 to  $\leq$ 75 years
- >75 to  $\leq$ 85 years
- >85 years

#### Treatment Variables 4.4.2

COPD medication will be categorized as inhaled corticosteroid (ICS), long-acting beta agonist (LABA), long-acting muscarinic antagonist (LAMA), ICS-LABA, LAMA-LABA, ICS-LAMA-LABA, short-acting beta agonist (SABA), short-acting muscarinic antagonist (SAMA), SAMA/SABA, phosphodiesterase 4 (PDE4) inhibitors, methylxanthines, therapies, or other based on the COPD Medication Categorization List in Appendix B. This section will be updated as necessary if new COPD therapies become available over the course of the study and are added to the eCRF.

#### Pre-Study Treatment

Pre-study treatment will be categorized into one of the qualifying maintenance therapies (LAMA monotherapy, LABA monotherapy, ICS/LABA fixed dose combination (FDC)) according to the COPD Medication Categorization List in Appendix B.

#### **On-Study** Treatment

Triple therapy is defined as any of the combination of ICS, LABA and LAMA drugs that a patient's physician chooses. Therefore, the following combination of COPD medications categories will count as triple therapy on study, differentiating between free combination and FDC:

- Triple Therapy Free Combinations
  - $\circ$  ICS + LABA + LAMA
  - ICS-LABA + LAMA
  - ICS + LAMA-LABA
- Triple Therapy FDC
  - o LAMA-LABA-ICS

Patients may switch or discontinue study treatment over the 12 month observation period.

For the purpose of analysis, patients will be classified as Continued Original Randomized Treatment, Continued In-Class Randomized Treatment, or Off Randomized Treatment as described below. The categories are non-overlapping. Changes in targeted COPD concomitant medications do not apply to this classification.

- **Continued Original Randomized Treatment**: Patients taking the same COPD medication as originally initiated for randomized COPD study treatment.
  - Stiolto Respimat patients taking Stiolto Respimat.
  - Triple Therapy patients taking the same individual components of ICS plus LAMA plus LABA as initiated at Baseline.
- Continued In-Class Randomized Treatment: This definition only applies to Triple Therapy patients who made changes to the triple therapy components originally initiated for their randomized COPD study treatment (i.e., those not considered "Continued Original Randomized Treatment").
  - Triple Therapy patients taking any combination of ICS plus LABA plus LAMA that meets the study definition of triple therapy will be considered "Continued In-Class Randomized Treatment" if changed from original study medications.

•

- **On Treatment**: Patient is categorized as Continued Original Randomized Treatment or Continued In-Class Randomized Treatment (the duration of time is from randomization until the patient is no longer in one of these two categories)
  - Patients who have a temporary treatment interruption of  $\leq 28$  days will still be considered On Treatment provided they resume treatment that meets the On Treatment definition within 28 days of when the treatment was first interrupted.
    - If the On Treatment study medication is resumed with a new start date ≤ 28 days of the stop date, it will be classified as a temporary treatment interruption.
    - If the On Treatment study medication is resumed with a new start of >28 days of the stop date, or if the On Treatment study medication is not resumed before EOS or last contact, it will be classified as a treatment discontinuation.
    - For Triple Therapy patients, a >28 day continuous window in which they are not receiving all 3 components of triple therapy will be considered treatment discontinuation. This could occur due to a >28 treatment interruption of a single component, or overlapping treatment interruptions of more than one component such that the patient does not receive triple therapy for a continuous window of >28 days.
- **Off Randomized Treatment**: Patient is categorized as Off Treatment (the duration of time is from when the patient is no longer On Treatment until EOS or last contact)

On Treatment will also be used for the safety analysis (Section 6.3).

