6.6 Safety Analysis

[figure not shown]
Collection of AEs in the study eCRF will be limited to AEs leading to study treatment discontinuation or dose modification, or trial withdrawal. All SAEs will be reported by the investigator via a dedicated SAE report form directly to Boehringer Ingelheim Global Pharmacovigilance as described in [section 7.2](#). As hospitalization SAEs are reflected in claims records, a patient-level review comparing hospitalization claims entries with reported SAEs for each respective patient will take place after completion of the 12-month visit in order to identify any hospitalizations of which the investigator was potentially unaware. The investigator will receive information of any SAE identified through this process and report it using the standard SAE reporting process (See [section 7.2](#)).

SAE data for analysis will be drawn from the Boehringer Ingelheim Safety Database.

Analysis of non-serious AEs (leading to study treatment discontinuation or dose modification, or trial withdrawal) will be performed on the study database, as these are entered in the eCRF only.

Safety analyses will be descriptive in nature. No hypothesis testing is planned prospectively.

AEs will be coded using the current version of the Medical Dictionary for Regulatory Activities (MedDRA) coding dictionary at the time of reporting, and recoded to the MedDRA version current at the time of database integration. Summary tables and listings will be produced to compare the incidence of AEs across treatment groups, by Preferred Term (PT)/System Organ Class (SOC) and also by medical concept (MedDRA Standardized Medical Queries (SMQ) or custom Boehringer Ingelheim searches termed Pharmacovigilance (PV) endpoints). All AEs with an onset after the first dose of trial medication and up to 21 days after the last dose of trial medication will be assigned to the on-treatment period. Other AEs will be assigned either to the screening period, post-treatment period or the post-study period as appropriate.

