# COPD Medication Class Categories

The following targeted COPD concomitant medications will be defined for descriptive summary of COPD concomitant medication use by class at Baseline and EOS or last contact. Baseline COPD concomitant medications will be medications with "On-Study Concomitant" status designated in the eCRF and a start date on or prior to the patient's Baseline date. EOS COPD concomitant medications will be medications designated "On-Study Concomitant" in the eCRF with a status of "Ongoing" at EOS or the latest medication entry.

*Targeted COPD Concomitant Medications* at Baseline and EOS (Patients could contribute to multiple categories)

- SABA only
- SAMA only
- SAMA + SABA (free or FDC)
- PDE4 Inhibitors
- Methylxanthines
- Oxygen

• Not taking any targeted COPD concomitant medications

The following Study COPD medication class categories will also be defined for descriptive summary of Study COPD medication at EOS or last contact:

Study COPD Medications at EOS (Categories are non-overlapping)

- LAMA only
- LABA only
- LAMA + LABA
- ICS + LABA
- ICS + LAMA + LABA
- ICS-LAMA-LABA (FDC)
- Not taking any Study COPD Medications
- Discontinued all COPD Treatment: Patients not taking any COPD medication at EOS (no Study COPD medication use and no targeted COPD concomitant medication use).

Additionally, the following definitions described below will descriptively report changes in Study COPD medication at EOS or last contact.

- **Original Randomized Treatment**: Patients taking the same COPD medication at EOS as originally initiated for randomized COPD study treatment.
  - Stiolto Respimat patients taking Stiolto Respimat.
  - Triple Therapy patients taking the same individual components of ICS plus LAMA plus LABA as initiated at Baseline.
- Step-Over In-Class Randomized Treatment: This definition only applies to patients taking different treatment components at EOS as originally initiated for their randomized COPD study treatment (i.e., those not considered "Original Randomized Treatment").
  - Triple Therapy patients taking any combination of ICS plus LABA plus LAMA that meets the study definition of triple therapy at EOS will be considered "Step-Over In-Class Randomized Treatment" if changed from original study medications.
  - Stiolto Respimat patients taking a LAMA plus LABA regimen at EOS other than Stiolto Respimat.
    - 4.4.3 CAT

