#### 6.3 Reporting and Analysis Periods

AEs and SAEs will be reported from the time a patient signs consent until the EOS visit at 12 months or until the patient discontinues the trial. However, only "on treatment" AEs and SAEs will be included in analysis. "On treatment" medications for each treatment arm are defined in section 4.4.2. For the safety analysis time period, all AEs will be considered "on treatment" (see section 4.4.2) if the AE start date is within 21 days after the On Treatment study medication end date or until EOS, whichever comes first.

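### Does SAP 4.4.2 leave open whether a Stiolto patient who adds an ICS is still On Treatment for the safety tables?

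*SAP*

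**What the plan says.** SAP 4.4.2 (On-Study Treatment) puts a patient in the category Continued Original Randomized Treatment under the general line "Patients taking the same COPD medication as originally initiated for randomized COPD study treatment". The line for the experimental arm is "Stiolto Respimat patients taking Stiolto Respimat". The section also states "Changes in targeted COPD concomitant medications do not apply to this classification". The targeted concomitant list, under COPD Medication Class Categories, does not include ICS. ICS plus a LAMA-LABA is one of the listed free-combination triple therapies, and Appendix B files Stiolto under LAMA-LABA.

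On Treatment runs from randomization until the patient leaves the qualifying categories. An interruption becomes a discontinuation when study medication is stopped and not resumed within 28 days. For the triple arm, a longer-than-28 "day continuous window in which they are not receiving all 3 components of triple therapy will be considered treatment discontinuation".

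SAP 6.3 takes its on-treatment medications for each arm from 4.4.2 and says that only on-treatment "AEs and SAEs will be included in analysis". An event qualifies "if the AE start date is within 21 days after the On Treatment study medication end date", capped at end of study (EOS). Protocol 6.6 says that events with onset after the first dose and "up to 21 days after the last dose of trial medication will be assigned to the on-treatment period".

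For the EOS summary, Original Randomized Treatment repeats the wording: "Patients taking the same COPD medication at EOS as originally initiated for randomized COPD study treatment".

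**The concern.** Adding an ICS to Stiolto is foreseeable. Patients enter uncontrolled, are treated by routine judgment, and may change treatment. Such a patient is then taking a regimen that the SAP itself calls triple therapy.

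The general line can be read to end On Treatment at that point, because the overall medication is no longer the same as at the start. The Stiolto line can be read to continue it. The exemption for concomitant drugs does not decide the matter, since ICS is not a targeted concomitant. The triple arm has an explicit rule for losing a component, and the Stiolto arm has no visible rule for gaining one.

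If the ICS ended On Treatment, two problems could follow:

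- SAP 6.3 counts from a medication end date, and a drug still being taken has none.
- If the window were closed 21 days after ICS start instead, SAEs and deaths in patients still on Stiolto would drop out of the summary tables. That would depart from the protocol's last-dose rule, and SAP 2.1 announces no such change.

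The trial is open-label with an unblinded database, so an unstated classification rule deserves a check.

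**Working it through.** The plan gives no figure on this point, so there is nothing to reproduce. The check is to apply the rules to one patient and then to bound the effect.

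**Which reading does the text support?**

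1. The general line in 4.4.2 is tied to the drug started as the randomized study treatment. For this arm that drug is Stiolto, and the patient still takes it.
2. The arm-specific line asks only whether a Stiolto patient takes Stiolto. The answer is yes.
3. The discontinuation rule is driven by stop and restart dates of study medication. Adding a drug triggers neither.
4. SAP 6.3 refers to 4.4.2 for each arm's on-treatment medications, then counts from the end date of that medication. For this patient that is the Stiolto stop date.
5. Protocol 6.6 counts from the last dose of trial medication, which gives the same date.

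All five agree on still On Treatment. The separate rule for the triple arm has a simple reason: three components can stop at different times, whereas Stiolto is one product. In the visible text the list of triple combinations is used only to classify patients randomized to triple therapy.

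**One patient.** The ICS is added on day 90 and Stiolto continues to day 365.

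| Application | Window ends | Days excluded |
|---|---|---|
| Still On Treatment | EOS | 0 |
| Off at ICS start, SAP 6.3 taken literally (Stiolto has no end date) | EOS | 0 |
| Off at ICS start, category end used as the end date in SAP 6.3 | 90 + 21 = day 111 | 365 − 111 = 254 |

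The two feared problems therefore do not occur together. With no end date, nothing is lost. Events are lost only if the category end in 4.4.2 is put in place of the medication end date that SAP 6.3 names.

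**Size under that third application.** Stiolto arm: 703 / 2 = 351.5 patients (SAP 2.1 gives about 703; allocation is 1:1). Assumed, because the documents do not say: a share f adds an ICS, start dates are uniform over the year, there is no dropout, and a share s has an SAE per year.

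- Mean fraction of the year excluded per affected patient: (365 − 21)² / (2 × 365²) = 118,336 / 266,450 = 0.444.
- Patient-years excluded: 351.5 × f × 0.444 = 7.8, 15.6 and 31.2 for f = 5%, 10% and 20%.
- Share of the arm's person-time: f × 0.444 = 2.2%, 4.4% and 8.9%.
- Patients with an excluded SAE, 351.5 × f × 0.444 × s: from 0.8 (f = 5%, s = 10%) through 3.1 (f = 10%, s = 20%) to 9.4 (f = 20%, s = 30%).

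**The case for a change.** The strongest case for a change is that no visible sentence names the added ICS, that the SAP ends the period by category in 4.4.2 but by medication end date in 6.3, and that the two can differ for exactly this patient. The EOS definition repeats the same wording where nothing appears to have been removed. There, the class table would show the patient under ICS + LAMA + LABA while the change table could show Original Randomized Treatment. Even a few lost cases could include deaths, and one sentence would settle it.

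Part of this stands. The case is not named, and a sentence saying that On Treatment for this arm lasts until Stiolto is stopped would do no harm. But the reading that causes the damage is the one that makes SAP 6.3 hard to apply and contradicts Protocol 6.6, which is good reason for an analyst not to adopt it. SAP 2.1 lists no departure from the protocol because the plain reading makes none. An empty bullet stands just before the On Treatment definition, and Off Treatment is used without a visible definition, so removed text may already cover the case. The two EOS tables answer different questions: which classes a patient takes, and whether the assigned drug was kept. A patient on Stiolto plus ICS can properly appear in both.

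The remaining protections are also real. SAP 5.0 limits review before database lock to unpopulated table shells. SAEs go to the sponsor however they are later classified. SAP 6.4.1 provides a listing of all SAEs, although whether the SAP 6.3 restriction applies to it is unclear. A separate column for Stiolto plus ICS would be a group defined after randomization, with small counts and no comparator. Wanting it is a matter of preference.

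**Conclusion.** The concern does not call for a change. The visible text omits a detail that a competent analyst would fill in one way: the patient stays On Treatment until Stiolto itself stops, and the 21-day window runs from that date. This agrees with Protocol 6.6 and excludes no events.

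The price is that some Stiolto-plus-ICS time is counted in the Stiolto column. That is acceptable for descriptive safety tables without testing, and the EOS class table shows by arm how many patients were on all three classes at the end. It does not show those who added an ICS and stopped it earlier.

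The possible loss of about 1 to 9 patients' SAEs rests on assumed add-on and SAE rates and on a reading the text does not favour; on the plain reading it is zero. The primary and secondary intent-to-treat analyses do not use this classification. The on-treatment exacerbation sensitivity analysis mentioned in Protocol 6.2.1.2 might use it, but its details are not visible and it cannot be judged here.

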# 6.4.1 AE Analysis

AE analyses will be descriptive in nature. No hypothesis testing is planned prospectively. All analyses of AEs will be based on the number of patients with AEs and NOT on the number of AEs.

SAE data will be drawn from the Boehringer Ingelheim Safety Database, while other AEs collected as per protocol through the eCRF will be drawn from the study database. AE data for analysis will be merged from all sources for analysis.

AEs will be coded using the current version of the Medical Dictionary for Regulatory Activities (MedDRA) coding dictionary at the time of reporting. Summary tables and listings will be produced to compare the incidence of AEs across treatment groups, by Preferred Term (PT)/System Organ Class (SOC).

The frequency and percentage patients experiencing AEs and SAEs will be summarized by SOC and PT for the safety population overall and by treatment group as follows:

- All collected AEs, regardless of seriousness, relatedness, or collection context
- AEs leading to study treatment discontinuation, dose modification or trial withdrawal
- AEs leading to study treatment discontinuation (subset of the above table)
- AEs with a reasonable causal relationship to study treatment
- All SAEs
- Fatal AEs (subset of all SAEs)
- Listing of all SAEs

There will be no subgroup analyses for safety.

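### On Treatment is defined by class for triple therapy but by product for Stiolto, so the crude AE percentages compare safety windows that are unequal by rule

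*SAP*

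**What the plan says.** Under On-Study Treatment, SAP 4.4.2 gives a patient two routes to being On Treatment: continuing the original randomised treatment, or continuing in class.

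- The in-class route is limited to Triple "Therapy patients who made changes to the triple therapy components originally initiated". Under it, "Triple Therapy patients taking any combination of ICS plus LABA plus LAMA that meets the study definition of triple therapy will be considered" continued in class, so a triple patient may change products and remain On Treatment while the regimen still contains ICS, LABA and LAMA.
- For the other arm, the only qualifying group is "Stiolto Respimat patients taking Stiolto Respimat".
- On Treatment time is defined thus: "the duration of time is from randomization until the patient is no longer in one of these two categories". An interruption of up to 28 days is tolerated "provided they resume treatment that meets the On Treatment definition within 28 days of when the treatment was first interrupted".
- A further rule applies to the triple arm only: a continuous gap of more than 28 days without all three components counts as discontinuation.

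Later in 4.4.2, under COPD Medication Class Categories, the descriptive EOS category Step-Over In-Class includes "Stiolto Respimat patients taking a LAMA plus LABA regimen at EOS other than Stiolto Respimat".

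SAP 4.4.2 carries On Treatment into the safety analysis. SAP 6.3 restricts that analysis to on-treatment AEs and SAEs, ending 21 days after On Treatment medication stops or at EOS, whichever is sooner. SAP 6.4.1 compares AE incidence across arms as frequencies and percentages by SOC and PT, and adds: "All analyses of AEs will be based on the number of patients with AEs and NOT on the number of AEs". The visible text has no person-time, exposure-adjusted rate or time-to-event output for AEs.

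**The concern.** Switching is expected in both arms: "Patients may switch or discontinue study treatment over the 12 month observation period". The same kind of change has opposite consequences for the safety window. A triple patient who replaces one or all products with others of the same classes keeps an open window. A Stiolto patient who moves to another LAMA-LABA listed in Appendix B, and does not resume Stiolto within 28 days, has a window that closes 21 days after Stiolto ends. Later events in that patient drop out of the analysis.

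A percentage of patients with an event depends on how long each patient is observed. If the rules give the arms different observation times, the percentages can differ although the underlying risk is the same. Randomisation does not protect against this, because the windows are defined after randomisation and differently by arm.

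The effect falls mainly on SAEs and fatal events. Non-serious AEs are collected only if they lead to treatment discontinuation, dose modification or trial withdrawal (protocol 6.6 and 7.1), so few would be recorded after study treatment has stopped.

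**Working it through.** The plan states no figure on this point, so there is none to reproduce. The check traces the rules through to the tables and then sizes the in-class rule on its own.

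**Same change, two arms**

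| Change during the year | Triple arm | Stiolto arm |
|---|---|---|
| Other products, same classes | On Treatment | Off 21 days after Stiolto ends, unless resumed within 28 days |
| More than 28 days without one component | Off | No separate rule (single product) |
| EOS description of an in-class change | Step-Over In-Class | Step-Over In-Class |

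**Inputs**

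- From the documents: 12 months of follow-up whatever the treatment changes (protocol 5.4 and 5.7.2), taken as 365 days; a 21-day tail capped at EOS (SAP 6.3).
- Assumed, because the documents do not give them: true 12-month risk of 15% in both arms with constant hazard; a share *s* of each arm switching in class; switch time *T* uniform over the year and independent of events; no other discontinuation in either arm.

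**Window lost per switcher**

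A Stiolto switcher's window is min(*T* + 21, 365). The mean loss is (365 − 21)² / (2 × 365) = 118,336 / 730 = 162 days. A triple in-class switcher loses 0 days.

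**Crude percentage**

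1. Hazard λ = −ln(0.85) = 0.1625 per year.
2. Probability of a counted event in a Stiolto switcher = 1 − [(e^(−21λ/365) − e^(−λ)) / λ + (21/365) e^(−λ)] = 1 − [(0.9907 − 0.8500) / 0.1625 + 0.0575 × 0.85] = 1 − 0.9146 = 8.54%.
3. Stiolto percentage = (1 − *s*) × 15% + *s* × 8.54%. The triple percentage stays at 15.0%.

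| *s* | Mean Stiolto window (days) | Stiolto % | Triple % | Spurious ratio |
|---|---|---|---|---|
| 5% | 356.9 | 14.7 | 15.0 | 0.98 |
| 10% | 348.8 | 14.4 | 15.0 | 0.96 |
| 20% | 332.6 | 13.7 | 15.0 | 0.91 |
| 30% | 316.4 | 13.1 | 15.0 | 0.87 |

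True risks of 10%, 20% or 30% give nearly the same ratios: 0.98 at 5% switching and 0.87 to 0.88 at 30%.

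**The opposing rule**

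Suppose a share *g* of triple patients leave On Treatment through the three-component rule and lose the same average time. The net difference in mean window is then (*s* − *g*) × 162 days. It is zero at *g* = *s* and reverses when *g* > *s*. For example, *s* = 10% and *g* = 20% leaves the triple window shorter by 16.2 days.

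**Does exposure adjustment remove the distortion?**

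With constant hazard, expected time to first event or window end is P(event) / λ. This is 0.15 / 0.1625 = 0.923 years for a full window and 0.0854 / 0.1625 = 0.5255 years for a Stiolto switcher. At *s* = 20%, mean Stiolto person-time is 0.8 × 0.923 + 0.2 × 0.5255 = 0.8435 years, and the rate is 0.1371 / 0.8435 = 0.1625 per year. The true hazard is recovered. The same holds if the triple windows are the shorter ones.

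**The case against.** **The asymmetry follows the interventions.** One arm is a named product, the other any approved combination the physician chooses, so On Treatment means receiving the assigned intervention in both. This stands: a product-specific window is defensible for describing Stiolto's own safety. It does not make percentages over different windows comparable, and SAP 6.4.1 says the tables are for comparing arms.

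**The EOS category is not a rival safety rule.** A reader might infer that 4.4.2 contradicts itself. It does not: Step-Over In-Class only describes medication changes at EOS. It does show that the plan recognises the Stiolto in-class move, while the safety window makes no allowance for it.

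**The model overstates the loss.** It makes switching independent of events. The tables count patients, so someone who switches because of an SAE has already been counted in the SAE total and loses nothing there. This stands, and it makes the ratios illustrations rather than estimates.

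**The effect is small against the trial's precision.** With about 703 patients, an assumed even split and 15% risk, the standard error of the difference is √(2 × 0.15 × 0.85 / 351.5) = 2.7 percentage points. The illustrated distortion at 10–30% switching is 0.65 to 1.94 points, roughly 2 to 7 patients. Safety is descriptive and untested, and the primary and secondary effectiveness analyses are ITT and unaffected. All of this limits the weight of the point, but imprecision does not remove a systematic difference in the windows.

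**The public text is incomplete.** A blank bullet follows the in-class definition, and other outputs may have been removed. The visible wording nevertheless restricts the category to triple patients.

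**Conclusion.** The point holds as an inequality of safety windows by rule. It makes crude percentages, chiefly for SAEs and fatal AEs, not directly comparable between arms. Taken alone, the in-class rule lowers the Stiolto percentages by a factor of about 0.98 at 5% in-class switching and 0.96 to 0.87 at 10–30%, under the stated assumptions of equal true risk, constant hazard, and uniform switch times independent of events.

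Two stronger readings are tempting and unsupported. The first is that a triple patient who changes products necessarily stays On Treatment to EOS; the rule on more than 28 days without all three components can end it earlier. The second is that the safety tables are biased in favour of the sponsor's product. That triple-only rule works in the opposite direction, and the documents give no switching or interruption rates for either arm, so net size and direction are unknown. Not knowing them is itself a reason to report exposure.

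**What to change.** In SAP 6.4.1:

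1. Report on-treatment person-time by arm, including the 21-day tail and capped at EOS.
2. Beside each percentage, at least in the SAE and fatal-AE tables, show patients with a first event per 100 patient-years, with each patient's time stopped at the first event or the end of the window.
3. Base the descriptive comparison between arms on these rates. They correct for unequal windows in either direction, on the usual assumption of a roughly constant hazard.
4. Optionally, add one sensitivity table of SAEs and fatal AEs to EOS by randomised arm regardless of treatment changes, or with Stiolto patients who switch to another LAMA-LABA kept in. This should not replace the main table, because it attributes events on other products to the Stiolto arm.

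No new data are needed: treatment changes are recorded, and AEs and SAEs are reported to EOS or trial discontinuation. The cost is a few table columns and at most one extra table. The only downside is a slightly longer safety output.
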